8.3 Study Drug Packaging, Labelling, and Blinding

8.3.1 Packaging and Labelling

Study drug will be labelled appropriately as investigational product for this study. Packaging and labelling will be prepared to meet all local regulatory requirements.

8.3.2 Blinding and Randomization of Study Drug

Blinding is not applicable as this is an open-label study. All patients will take A3907 administered orally once daily at approximately the same time each day as described in [Section 8.2](#). Patients will be assigned to treatment arms via an interactive voice/web response system (IXRS).

Patient Identification

After written informed consent is obtained from an eligible patient, an 8-digit patient identification number will be assigned. The first 2 digits will denote the country, followed by a 3-digit site number and a 3-digit patient sequence number. This number will be captured by the IXRS and integrated into the eCRF in Protocol A3907-002.

8.3.3 Procedure for Breaking the Blind

Not applicable as this is an open-label study.

8.4 Patient Compliance

Study drug compliance will be monitored through Patient Diary entries. Any noncompliance will be documented in the source documents. Additionally, patients will return all unused study drug at Visit 4, Visit 5, Visit 6, and Visit 7. The study site staff will count all returned drug, assess compliance, and record drug accountability.

8.5 Study Drug Accountability

Accountability for the study drug at the study site is the responsibility of the investigator (or designee). The investigator (or designee) will ensure that the study drug is used only in accordance with this protocol. Where allowed, the investigator (or designee) may choose to assign drug accountability responsibilities to an appropriate individual.

The investigator (or designee) will maintain accurate study drug accountability records indicating the drug's delivery date to the site, inventory at the site, use by each patient, and return to the sponsor or its designee (or disposal of the drug, if approved by the sponsor). These records will adequately document that the patients were provided the doses as specified in the protocol and should reconcile all study drug received from the sponsor. Accountability records will include dates, quantities, batch numbers, expiration dates (if applicable), and patient numbers. The sponsor or its designee will review drug accountability at the site on an ongoing basis during monitoring visits.

Study drug must not be used for any purpose other than the present study. Study drug which has been dispensed to a patient and returned unused must not be re-dispensed to a different patient.

Patients will receive instructions for home administration of study drug along with a Patient Diary to confirm study drug administration.

All unused and used study drug will be retained at the site until they are inventoried by the study monitor. All used, unused, or expired study drug will be returned to the sponsor or its designee or if authorised, disposed of at the study site according to the site's Standard Operating Procedures and must be documented. All material containing study drug will be treated and disposed of as hazardous waste in accordance with governing regulations.

8.6 Concomitant Therapy and Prohibited Medications

All medications administered from screening to 14 days after the last dose of study drug are to be recorded on the eCRF. All medications, including vitamin supplements, over-the-counter medications, and herbal preparations, as well as non-drug therapies, taken throughout the study must be documented in the patient's source documents and eCRF.

All medications taken by a patient within 14 days or 5 times the half-life of the drug, whichever is longer, prior to the first intake of study drug are regarded as prior medication. All medications taken by a patient on or after the first day of study drug intake, and which continue to be taken during the study, are regarded as concomitant medication.

Patients will be instructed not to take any additional medications during the study without prior consultation with the treating physician. At each visit, the patient will be asked about any new medications he/she is taking or has taken after the start of the study drug.

8.6.1 Permitted Medications

The following concomitant medications are permitted:

- In patients with IBD, in the event of an IBD flare, up to 25 mg of prednisone per day or 9 mg of budesonide/budesonide MMX or 10 mg of beclomethasone may be taken without jeopardizing their participation in the study. Mesalamine or beclomethasone enemas are also admitted medications. If a higher dose of prednisone or a biological agent is needed or the patient needs to be hospitalised for controlling disease activity, then the patient's participation in the study is to be terminated.
- If a patient is taking cholestyramine at the Screening Visit, they should remain on a stable dose during the study, and it should be taken 4 hours after administration of A3907 study drug.
- UDCA is permitted with a total daily dose ≤ 23 mg/kg/day, a minimum of 3 months of stable treatment prior to the Screening Period, and expected to remain on a stable dose through the 12-week treatment period. However, UDCA should not be taken within 4 hours of A3907.
- Vitamin D or fibrates are permitted. Patients must be on a stable dose for at least 6 months prior to starting treatment with A3907.
- Approved vaccines are permitted during the trial.

8.6.2 Excluded Medications and Substances

The following medications are prohibited:

- Medications that slow GI motility (e.g. sucralfate, loperamide, codeine)
- Statins
- Immunosuppressive medication for controlling IBD (e.g. azathioprine, 6 mercaptopurine, tacrolimus, methotrexate, infliximab, adalimumab, golimumab, vedolizumab, ustekinumab, tofacitinib, ozanimod)

Patients will be instructed not to take any of the following medication for 14 days or 5 times the half-life of the drug, whichever is longer, prior to receiving the first dose of the study drug:

- Oral drugs that are strong inhibitors or inducers of CYP3A4 enzymes (e.g. grapefruit juice, ritonavir, itraconazole, ketoconazole, troleandomycin, rifampin, St John's wort, etc.)

Patients will be instructed not to take any of the following medication during the study:

- Oral drugs that are a substrate of CYP3A4 enzymes (e.g. codeine, ciclosporin [cyclosporin], diazepam, etc.)
- Oral drugs that are a substrate of P-gp or breast cancer resistance protein transporters
- Drugs that are a substrate of OATP1B1

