 - b. liver stiffness measurement, assessed by FibroScan (FibroScan value > 14.4 kPa), in addition to clinical assessment and biochemical markers at the discretion of the investigator.
 - c. signs and symptoms of hepatic decompensation (including, but not limited to, jaundice, ascites, variceal haemorrhage, and/or hepatic encephalopathy).
15. History of bacterial cholangitis within 60 days prior to the Screening Period, or if the patient is on antibiotics for prophylaxis of recurrent cholangitis.
16. Females who are pregnant, lactating, or breast feeding as detailed in [Section 9.3.18](#).
17. History of alcohol or substance abuse in the previous 2 years. Patients must agree to refrain from illicit drug (including marijuana) and alcohol use during the study.
18. Hypersensitivity to investigational medicinal product (A3907) and its excipients.
19. Presence of any contraindication for undergoing MRCP (e.g. pacemaker).
20. Any other condition or abnormality which, in the opinion of the investigator (or designee), may compromise the safety of the patient or interfere with the patient participating in, or completing the study.

Treatment Exclusions:

21. Administration of medications that slow gastrointestinal motility ([Section 8.6.2](#)).
22. Treatment with rifampicin.

23. Exposure to oral drugs that are strong inhibitors or inducers of CYP3A4 enzymes (e.g. grapefruit juice, ritonavir, itraconazole, ketoconazole, troleandomycin, rifampin, St John's wort, etc.) within 14 days prior to the Screening Period, or 5 half-lives of the drug, whichever is longer ([Section 8.6.2](#)).
24. Exposure to oral drugs that are substrates of CYP3A4 enzymes (e.g. codeine, ciclosporin [cyclosporin], diazepam, etc.) during the study ([Section 8.6.2](#)).
25. Treatment with vitamin D or fibrates, unless patient is on a stable dose ≥ 6 months prior to baseline.
26. Exposure to an investigational drug, biologic agent, or medical device within 30 days prior to the Screening Period, or 5 half-lives of the study agent, whichever is longer.

Laboratory Exclusions:

27. Platelet count $< 150\,000/\text{mm}^3$.
28. Albumin level $< 3.0\text{ g/dL}$.
29. INR > 1.3 (the patient may be treated with vitamin K intravenously, and if INR is ≤ 1.3 at resampling, the patient may be enrolled).
30. Medical conditions that may cause non-hepatic increases in ALP (e.g. Paget's disease). A GGT or ALP isoenzymes should be obtained for confirmation of biliary origin;

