9.3.16 Special Situations

Certain safety events are defined by regulatory authorities as special situations and require reporting. These special situations include:

- Overdose of study medication ([Section 9.3.17](#))
- Pregnancy ([Section 9.3.18](#))
- Suspected abuse/misuse of study medication
- Medication error involving the study medication
- Drug-drug interaction

Special situations should be reported within 24 hours of awareness on the Special Situations eCRF, whether or not they result in an AE/SAE. If a Special Situation results in

an AE or SAE, the event should also be reported on the AE/SAE eCRF following the process described in [Section 9.3.4.8](#).

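### Oral strong CYP3A4 inhibitors and inducers are barred before the first dose, but no readable rule bars them during the 12 weeks of dosing that a single post-washout exposure check permits

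*Protocol*

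**What the plan says.** Two protocol rules deal with oral strong CYP3A4 inhibitors and inducers as a class.

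- Exclusion 23 (Section 7.2.3, repeated in the synopsis) bars exposure "within 14 days prior to the Screening Period, or 5 half-lives of the drug, whichever is longer".
- Section 8.6.2 states: "Patients will be instructed not to take any of the following medication for 14 days or 5 times the half-life of the drug". It takes the longer of the two periods and ends the restriction at the first dose.

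Section 8.6.2 then opens a separate list: "Patients will be instructed not to take any of the following medication during the study". That list covers substrates: of CYP3A4, of OATP1B1, and "Oral drugs that are a substrate of P-gp or breast cancer resistance protein transporters". Exclusion 24 likewise concerns substrates: "Exposure to oral drugs that are substrates of CYP3A4 enzymes (e.g. codeine, ciclosporin [cyclosporin], diazepam, etc.) during the study". The general prohibited list at the head of 8.6.2 names drugs that slow GI motility, statins, and immunosuppressants for IBD.

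Sections 5.4 and 5.5 describe the exposure safeguard. Each patient is dosed on Day 0, the individual profile is compared with the highest exposure in the single-dose part of the first-in-human study, and 12 weeks of dosing follow only if that exposure is not exceeded.

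**The concern.** Substrates matter chiefly if A3907 alters other drugs. Inhibitors and inducers matter if other drugs alter A3907. The protocol restricts the second group before dosing and lets the express restriction lapse when dosing begins, which is when a change in A3907 exposure would count.

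The Day 0 check is the protocol's stated protection against PK variability and against exceeding earlier human exposure. It is passed with this class washed out and then relied on for 12 weeks. An inhibitor started in that time could raise exposure above what was checked. An inducer could lower it, and one affected patient is 1/6, or 17%, of an arm. Section 5.5 notes that this is the first use of A3907 in PSC and that the risks in these patients are unknown.

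New anti-infective prescriptions on treatment are foreseeable. An exploratory endpoint (Section 6.2.3) counts cholangitis episodes that need antibiotics after dosing, and five of the seven examples of the class in 8.6.2 are anti-infectives: ritonavir, itraconazole, ketoconazole, troleandomycin and rifampin.

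**Working it through.** The plan gives no figure to reproduce. The check sets the rules side by side and places them on the visit schedule. Days follow the protocol's numbering; SAP Section 11 renames Day 0 as Day 1.

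**1. Which rule applies when**

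| Rule | Drugs covered | Period covered |
|---|---|---|
| Exclusion 23 | Oral strong CYP3A4 inhibitors, inducers | Before Screening |
| 8.6.2, washout list | Same class | Before the first dose |
| 8.6.2, on-study list | CYP3A4, P-gp/BCRP and OATP1B1 substrates | During the study |
| Exclusion 24 | Oral CYP3A4 substrates | During the study |
| 8.6.2, general list | GI-motility drugs, statins, IBD immunosuppressants | No end date given |
| Exclusion 22 | Rifampicin only | No window given |

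No row covers inhibitors and inducers as a class after the first dose. Sections 8.6, 8.6.1 and 9.3.1 add no such rule. SAP Section 7.1 defines and summarises medications but restricts none.

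**2. Length of the gap** (Table 1 of the protocol)

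- Covered before dosing, using the 14-day windows and a full 14-day Screening Period: Day −28 to −14 (Exclusion 23) plus Day −14 to 0 (8.6.2) = 14 + 14 = 28 days.
- Repeated dosing without a class rule: Visit 3 (Day 14) to Visit 7 (Day 98) = 98 − 14 = 84 days.
- Day 0 to Day 14 also lacks a class rule, but after the Day 0 dosing it is a confirmation period without A3907. It is not counted as exposed time.

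**3. PK information during those 84 days** (Table 1, footnote h; Section 9.4)

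- Full profiles: Day 0 and Day 98, the last dosing day.
- Single pre-dose samples at Visits 3 to 6. The Visit 3 sample precedes repeated dosing, so three fall under it: Days 28, 42 and 70.
- Intervals from Day 14: 28 − 14 = 14, 42 − 28 = 14, 70 − 42 = 28, 98 − 70 = 28 days.
- A within-patient rise in the pre-dose concentration could signal an interaction. No readable rule prescribes action on such a rise. Section 7.2.4.1 acts on Cmax or AUC limits, and the end of its second exposure criterion is redacted.

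**4. What cannot be computed**

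The half-life, Tmax, first-in-human exposures and margin to the limit are redacted. No readable passage gives the share of A3907 clearance due to CYP3A4 or the likely frequency of such prescriptions. A numerical effect on exposure would rest wholly on assumed values, so none is given.

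**The case against.** The strongest reply is that the harm rests on an unstated premise. No readable passage says CYP3A4 clears A3907, and the variability factors named in Section 5.4 do not include interactions. This stands as a limit on what can be claimed. It does not remove the inconsistency: if the interaction is irrelevant the washout is unnecessary, and if it is relevant the washout should continue through dosing.

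The protocol also has more protection than its prohibited lists suggest:

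- Section 8.6: "Patients will be instructed not to take any additional medications during the study without prior consultation with the treating physician". All medication, including over-the-counter and herbal products, is recorded, so use would be visible at analysis.
- An inhibitor or inducer that is also a listed substrate is already barred on study. The documents do not say which drugs these are.
- Exclusion 22 covers "Treatment with rifampicin", but this is one drug in an entry criterion.
- Drug-drug interactions are special situations under Section 9.3.16: "Special situations should be reported within 24 hours of awareness on the Special Situations eCRF, whether or not they result in an AE/SAE".
- A PK sample is taken near the onset of hepatic events and, if possible, at any SAE. Liver interruption rules (9.3.6.1) and study stopping rules (7.2.4.3) also apply.
- Exclusion 15 removes patients on prophylactic antibiotics for recurrent cholangitis or with bacterial cholangitis within 60 days before Screening. This narrows the antibiotic argument.

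These reduce the risk. However, a physician who consults 8.6.2 about a new prescription finds only a pre-dose washout for this class, and the PK, liver and stopping rules act after exposure has changed.

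Three stronger readings are tempting and not supported. A reader might infer that such a drug would push patients past the exposure limit, but both the margin and the size of the effect are unknown. A reader might count all 98 days from Day 0, but about 14 of them have no A3907 dosing. A reader might dismiss the pre-dose samples as uninformative. They give no AUC and are a weak test against a Cmax limit, but compared within a patient they can carry a signal.

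**Conclusion.** The gap is real and should be fixed. As written, the express restriction on oral strong CYP3A4 inhibitors and inducers ends at the first dose, and no readable rule restores it for the 84 days of repeated dosing. The one individual exposure check that permits this dosing was passed under washout of the class.

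The conclusion about the rules rests on the text alone. The consequence rests on one inference, that the sponsor's washout reflects a relevant effect of CYP3A4 on A3907. It is a possible change in exposure in either direction, of unknown size and frequency. The documents do not show that the exposure limit would be breached, nor that such prescriptions would be common.

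**What to change.** In Section 8.6.2, extend the restriction on oral strong CYP3A4 inhibitors and inducers, including grapefruit juice and St John's wort, from the existing washout through the last dose and the end of the Visit 7 PK profile. Leave the pre-dose windows as they are. Add that A3907 is stopped if a drug of this class becomes necessary. Section 8.2 already discontinues a patient who is off A3907 for more than 5 half-lives, so a temporary interruption would seldom be a workable alternative. The half-life is redacted, so the permitted gap cannot be stated in hours.

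The cost is one line and one sentence in a protocol amendment, with no new visits or samples and no SAP change. The downside is that an occasional patient would discontinue. Under Section 7.1.1 that patient may be replaced, unless the discontinuation is classed as due to an adverse event. Cholangitis that needs treatment could be classed that way, and the arm would then lose one of its six patients.

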9 STUDY ASSESSMENTS

9.1 Informed Consent

A complete description of the study is to be presented to each potential patient and a signed and dated informed consent is to be obtained before any study-specific procedures are performed.

9.2 Demographic Data and Medical History

Demographic information per country regulations, along with medical and surgical history, will be obtained and recorded in the eCRF at Visit 1.

Demographic data collected will include year of birth, age, gender, fertility status for females, and geographic origin. Geographical origin information will be collected in order to evaluate if the outcome is consistent across different sub-groups.

A complete medical and surgical history, including the date of diagnosis of PSC and prior investigational medications for PSC, will be obtained during the Screening Period. The medical history is to include all relevant prior medical history as well as all current medical conditions.

9.3 Safety Assessments

The timing and frequency of safety assessments are described in [Section 7.1.2](#) and [Section 7.1.3](#).

The primary safety analysis for this study will include the incidence of TEAEs, TEAEs leading to discontinuation, and TEAEs categorised by causality, severity, and seriousness assessments.

Trends in safety will also be evaluated for the following assessments:

- Concomitant medications
- Physical examinations
- Vital signs
- Laboratory test results (including clinical chemistry, hematology, urinalysis, and coagulation)

9.3.1 Concomitant Medications

Concomitant medications will be documented in the eCRF for each patient at each scheduled visit. All medications or non-drug therapies administered within 14 days before

the first day of study drug administration should be reported as prior medication in the eCRF. Subsequently, at each study visit, patients will be asked whether they have taken any medication other than the study medication (from the Screening Period through the end of the study). All medications, including vitamin supplements, over-the-counter medications, and oral herbal preparations, as well as non-drug therapies, taken on or after the first day of study drug dose through 14 days after the last dose of study drug must be documented.

Permitted and excluded medications are found in [Section 8.6](#).

9.3.2 Physical Examination

A physician or suitably trained qualified assistant will perform a complete physical examination at times presented in [Table 1](#).

A complete physical examination will include assessment of general appearance, eyes, ears, nose, throat, head/neck/thyroid, lymph nodes, cardiovascular, lungs/chest, abdomen, genitourinary, extremities, skin, musculoskeletal, and neurologic system; any other findings will also be documented. Height and weight will also be documented; height will be measured at the Screening Visit only.

9.3.3 Vital Signs

Vital sign measurements, including systolic and diastolic blood pressure, pulse rate, and temperature will be obtained at times presented in [Table 1](#).

Assessments should be conducted while the patient is seated. Vital sign measurements should be taken before A3907 administration.

9.3.4 Adverse Events

9.3.4.1 Safety Reporting Period

Each patient must be carefully monitored for the development of AEs during the safety reporting period.

The safety reporting period for AEs is from signing of the ICF through the last planned study visit or 14 calendar days after the last dose of the study drug, whichever occurs later.

An SAE that occurs following the safety reporting period and which is assessed by the investigator (or designee) as related to study medication should also be reported.

9.3.4.2 Definitions and Investigator Assessments

An AE is defined as any untoward medical occurrence in an enrolled patient regardless of causal relationship with study drug. An AE can therefore be any clinically significant unfavorable and unintended sign, symptom, or disease that occurs during the study, whether or not related to the study drug.

A TEAE in this study is any AE or worsening of an existing disease that occurs after the first dose of study drug and within the 14-day follow-up.

9.3.4.3 Clinical Significance

The investigator (or designee) will review all patient-reported events, laboratory and other test results and use clinical judgment to identify events that are clinically significant. Clinical significance is defined as any abnormal finding that results in further clinical investigation(s), treatment(s), or the diagnosis of a new condition. Patient reported events and protocol mandated laboratory values, vital signs, and physical examination findings can be considered clinically significant (i.e. an AE) if there is a deterioration compared to baseline. Examples of clinically significant worsening from baseline could include, but is not limited to, events causing withdrawal from the study and events requiring medical intervention outside of the study causing apparent clinical manifestations or judged relevant by the investigator (or designee).

9.3.4.4 Serious Adverse Events

Each AE must be classified by the investigator (or designee) as either serious or nonserious. This assessment is made independently of severity assessment. Any AE that meets any 1 of the following criteria is considered an SAE:

- The outcome of the AE is **death**.
- The AE is **life-threatening**, meaning that the patient is, in the opinion of the investigator (or designee), at immediate risk of death from the reaction as it occurred. This does not include an AE that, if more severe, might have caused death.
- The AE results in persistent or significant **disability/incapacity**. Disability means a substantial disruption of a person's ability to conduct normal life functions.
- The AE requires or prolongs **hospitalisation**. In-patient hospitalisation is defined of any stay in the hospital of more than 24 hours, or any admission to a hospital ward or unit as an inpatient.

- Hospitalisations for procedures that were planned prior to study participation are not considered SAEs.
- Hospital admissions for routine diagnostic testing not associated with an AE (e.g. admission due to travel distance) are not considered SAEs.
- The AE results in a **congenital anomaly/birth defect**.
- **The AE is an important medical event.** The investigator (or designee) should apply medical and scientific judgment to assess whether an AE should be classified as serious due to medical significance, even if no other seriousness criteria is met. As a general guideline, medically important events may significantly jeopardise the patient, represent a significant hazard, or require medical/surgical intervention to prevent one of the outcomes listed above. Examples of potential SAEs based on this criterion include, but are not limited to, allergic bronchospasm requiring intensive treatment in an emergency room or at home, blood dyscrasias or convulsions, even if they do not result in inpatient hospitalisation, or the development of drug dependency and drug abuse.

Seriousness assessment is made independently of severity assessment ([Section 9.3.4.5](#)). For example, a severe rash may not meet serious criteria as defined above and, therefore, would be considered a severe, non-serious AE.

